To evaluate the effect of baricitinib 4-mg QD and background SoC therapy compared to placebo and SoC on SLE disease activity	
 • Proportion of patients achieving an SRI-4 response at Week 52, defined as: 
 • a reduction of ≥ 4 points from baseline in SLEDAI-2K score, and • No new BILAG A and no more than 1 new BILAG B disease activity score, and • No worsening (defined as an increase of ≥ 0.3 points [10 mm] from baseline) in the PGA of Disease Activity.
Major Secondary^c	
To evaluate the effect of baricitinib 4-mg QD plus SoC compared to placebo plus SoC on SLE disease activity	
 • Proportion of patients achieving an SRI-4 response at Week 24 • Proportion of patients achieving a LLDAS response at Week 52
To evaluate the corticosteroid sparing effect of baricitinib 4-mg QD plus SoC compared to placebo plus SoC	
 • Proportion of patients receiving >7.5 mg prednisone (or equivalent) at baseline able to decrease dose by $\geq 25\%$ to a prednisone equivalent dose of ≤ 7.5 mg/day maintained between Week 40 and Week 52
To evaluate the effect of baricitinib 4-mg QD plus SoC compared to placebo plus SoC on SLE flares	
 • Time to first severe flare over 52 weeks
To evaluate the effect of baricitinib 4-mg QD plus SoC compared to placebo plus SoC on PROs	
 • Change from baseline in Worst Pain NRS at Week 52 • Change from baseline in FACIT-Fatigue total score at Week 52

Primary and Major Secondary Objectives and Endpoints

Objectives	Endpoints (Variables)^a
To evaluate the effect of baricitinib 2-mg QD plus SoC compared to placebo plus SoC on SLE disease activity	
 • Proportion of patients achieving an SRI-4 response at Week 52 • Proportion of patients achieving an SRI-4 response at Week 24 • Proportion of patients achieving a LLDAS response at Week 52
To evaluate the corticosteroid sparing effect of baricitinib 2-mg QD plus SoC compared to placebo plus SoC	
 • Proportion of patients receiving >7.5 mg prednisone (or equivalent) at baseline able to decrease dose by $\geq 25\%$ to a prednisone equivalent dose of ≤ 7.5 mg/day maintained between Week 40 and Week 52

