6.4 Analysis Methods

The family-wise type I error rate (FWER) will be controlled at a 0.05 significance level for primary and major secondary endpoints using a prespecified graphical procedure (see Section 6.6). Unless otherwise specified, all other hypothesis testing will be conducted at a nominal significance level of 0.05.

For assessments of the primary endpoint and other binary efficacy and health outcomes endpoints, the following will be provided unless otherwise specified:

- Observed percentage for each treatment group along with the corresponding 2-sided 95% confidence interval (CI)
- The difference in percentages and 95% CI using the Newcombe-Wilson method without continuity correction, used for descriptive purposes
- The p-value and 95% (unless otherwise specified) CI for the odds ratio from the logistic regression model, used for primary statistical inference. The model will include the following explanatory variables: treatment, baseline disease activity (total SLEDAI-2K <10; ≥ 10), baseline corticosteroid dose (<10 mg/day; ≥ 10 mg/day prednisone or equivalent) and region (North America, Central/South America/Mexico, Europe, Asia and Rest of World). A Firth penalized likelihood will be used (Firth 1993), and
- If deemed necessary, additional analyses of categorical efficacy variables will be conducted to address sparse data or small sample sizes. The Fisher's exact test will be utilized if necessary.

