Treatment comparisons of continuous efficacy and health outcome variables, except for SLICC/ACR Damage Index, Patient's Global Impression of Change and Joint Stiffness Duration, will use a restricted maximum likelihood-based MMRM analysis. The model will include the following explanatory variables as fixed factors: treatment, baseline disease activity (total SLEDAI-2K <10; ≥ 10), baseline corticosteroid dose (<10 mg/day; ≥ 10 mg/day prednisone or equivalent), region (North America, Central/South America/Mexico, Europe, Asia and Rest of World), visit (as categorical variable), baseline value, treatment-by-visit interaction, and baseline value-by-visit interaction. The response variable will be change from baseline across postbaseline visits. Within-patient errors will be modeled using an unstructured covariance structure. If the model fails to converge, the following covariance structures will be implemented in the following order: heterogeneous Toeplitz, heterogeneous autoregressive (1) heterogeneous compound symmetry, and autoregressive. The least squares (LS mean) difference, standard error, p-value, and CIs will be reported. Type III tests for the LS means will be used for the statistical comparisons.

Treatment comparisons of SLICC/ACR Damage Index will be made using analysis of covariance (ANCOVA) with baseline value as covariate. For Patient's Global Impression of Change, the analysis of variance (ANOVA) will be applied. For both models, treatment, baseline disease activity (total SLEDAI-2K <10; ≥ 10), baseline corticosteroid dose (<10 mg/day; ≥ 10 mg/day prednisone or equivalent), and region (North America, Central/South America/Mexico, Europe,

Asia and Rest of World) will be included as the categorical factors. Type III tests for LS means will be used for statistical comparison between treatment groups. The LS mean difference, standard error, p-value, and 95% CI may also be reported.

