CLASI	
The CLASI is a validated instrument to assess cutaneous manifestations of SLE consisting of 2 scores:
 
 Activity Damage 	Total Activity Score	Calculated within tablet system with edit checks; no additional derivation.	
Within tablet system: If any item scores, but not all are missing then impute a score of 0 for the missing item(s).
 
For completely missing questionnaires, data can be carried forward if obtained within 36 days of visit; otherwise missing.

		Total Damage Score	Calculated within tablet system with edit checks; no additional derivation.	
Within tablet system: if any item scores, but not all are missing then impute a score of 0 for the missing item(s).
 
For completely missing questionnaires, data can be carried forward if obtained within 36 days of visit; otherwise missing.

Description and Derivation of Efficacy/Health Outcomes Measures and Endpoints

Measure	Description	Variable	Derivation/Comment	Definition of Missing
LLDAS	The LLDAS is a composite measure designed to identify patients achieving a state of low disease activity.	LLDAS	
 SLEDAI-2K \leq 4, with no activity in SLEDAI-2K major organ systems (CNS, Vascular, Renal, Cardiorespiratory and Constitutional), where “no activity” is defined as all items of SLEDAI-2K within these major organ systems equal to 0. No new features of Lupus disease activity in SLEDAI-2K compared to previous occurred visit, where the “new feature” is defined as any of the SLEDAI-2K 24 items changed from 0 to greater than 0. PGA \leq 1 Current prednisone or equivalent \leq 7.5 mg/day 	Missing if any component remains missing after each instrument level imputation rule is applied.
SFI Flare	The SFI uses the SLEDAI score, disease activity scenarios, treatment changes, and PGA to define mild/moderate and severe flares.	SFI Flare	Not derived; used as entered.	The absence of a flare record, or ‘Not Applicable’, both are indicative of no occurrence of flare.
		Annualized Flare Rate	Calculated as the number of SFI flares divided by the flare exposure time in days multiplied with 365.25.	No minimum data requirement.
		Time to First Flare	The time to first flare will be derived as the first date of most recent flare minus date of first administration of investigational product. If the subject did not have a flare, the time to first flare will be censored at the end of the flare exposure time	No minimum data requirement.

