	Proportion of patients with worsening in each BILAG individual organ systems versus baseline ^e	Logistic Regression, NRI	PP	Week 52 visit	Exploratory endpoint
PGA	Proportion of patients with no worsening in PGA (compared with baseline)	Logistic Regression, NRI+MI	PPCV	Week 52 visit	Secondary endpoint
		Logistic Regression, NRI	PP	Week 52 visit	Secondary endpoint
	Change from baseline in PGA score over time through Week 52 visit	MMRM	PP	Week 52 visit	Secondary endpoint
BICLA	Proportion of patients achieving BICLA response	Logistic Regression, NRI + MI	PPCV	Week 52 visit	Secondary endpoint
		Logistic Regression, NRI	PP	Week 52 visit	Secondary endpoint
		Logistic Regression, NRI	AC	Week 52 visit	Secondary endpoint

Description of Efficacy/Health Outcomes Analyses

Measure	Variable	Analysis and Imputation Method	Datapoint Sets	TPI*	Analysis Type
28 Tender/ Swollen Joint Count	Change from baseline in tender joint count	MMRM	PP	Week 52 visit	Secondary endpoint
	Change from baseline in swollen joint count	MMRM	PP	Week 52 visit	Secondary endpoint
CLASI Activity Score	The proportion of patients with \geq 50% reduction from baseline in total activity score ^f	Logistic Regression, NRI	PP	Week 52 visit	Secondary endpoint
SFI	Annualized severe flare rate	Negative binomial regression	PPCV	Through Week 52 visit	Secondary endpoint
		Negative binomial regression	PP		Supplemental
		Negative binomial regression	AC		Supplemental
	Annualized mild/moderate flare rate	Negative binomial regression	PP	Through Week 52 visit	Secondary endpoint
	Annualized flare rate (any severity)	Negative binomial regression	PP	Through Week 52 visit	Secondary endpoint
	Time to first severe flare	Cox regression	PPCV	Through Week 52 visit	Major secondary (Principal inference)
			PP		Supplemental
			AC		Supplemental
	Time to first flare (any severity)	Cox regression	PP	Through Week 52 visit	Secondary endpoint
LLDAS	Proportion of patients who achieve a LLDAS	Logistic Regression, NRI + MI	PPCV	Week 52 visit	Major secondary (Principal inference)
		Logistic Regression, NRI	PP		Supplemental
		Logistic Regression, NRI	AC		Supplemental

Description of Efficacy/Health Outcomes Analyses

Measure	Variable	Analysis and Imputation Method	Datapoint Sets	TPI*	Analysis Type

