Appendix 2. Summary Tables Related to Patient Characteristics

Variable	Continuous Summary	Categorical Summary ^a
Age ^b	Yes	<65 years, ≥ 65 to <75 years, ≥ 75 to <85 years, ≥ 85 years; <40 years, ≥ 40 years; ≥ 65 years; ≥ 75 years
Sex	No	Male, Female
Ethnicity (US only)	No	Hispanic/Latino, Non-Hispanic/Non-Latino
Race	No	American Indian/Alaska Native, Asian, Black/African American, Native Hawaiian or other Pacific Islander, White, or Multiple
Geographic Region	No	North America, Central/South America/Mexico, Europe, Asia, Rest of World
Country	No	By country
Height (cm)	Yes	None
Waist circumference (cm)	Yes	None
Weight (kg)	Yes	<80 kg, ≥ 80 kg <100 kg, ≥ 100 kg
BMI at Visit 2 ^c	Yes	Underweight (<18.5 kg/m ²), Normal (≥ 18.5 and <25 kg/m ²), Overweight (≥ 25 and <30 kg/m ²), Obese (≥ 30 and <40 kg/m ²), Severely obese (≥ 40 kg/m ²)
Alcohol Use	No	Never, Current, Former
Tobacco Use	No	Never, Current, Former
Caffeine Use	No	Never, Current, Former
Prior SLE Therapy		
Prior use of immunosuppressants ^d	No	Yes, No 0, 1, ≥ 2
Prior use of methotrexate ^d	No	Yes, No
Prior use of azathioprine ^d	No	Yes, No
Prior use of mycophenolate ^d	No	Yes, No
Prior use of corticosteroids ^d	No	Yes, No
Prior use of antimalarials ^d	No	Yes, No
Prior use of biologics ^d	No	Yes, No
Prior use of belimumab	No	Yes, No
Prior use of rituximab	No	Yes, No
Baseline Disease Characteristics		
Time since diagnosis of lupus (years) ^e	Yes	<1 year, ≥ 1 to <3 years, ≥ 3 year to <7 years, ≥ 7 years
Age at diagnosis of SLE ^f	Yes	<6, ≥ 6 to <10 year, ≥ 10 to <17 years, ≥ 17 year to <40 years, ≥ 40
Any flare at baseline, (SELENA-SLEDAI definition)	No	None, Mild/Moderate, Severe
SLEDAI-2K score	Yes	(<10 or ≥ 10)

Variable	Continuous Summary	Categorical Summary ^a
Physician's Global Assessment of Disease Activity score	Yes	Mild (>0 and <1.5), Moderate (≥1.5 to ≤2.5), Severe (>2.5)
Total systemic Lupus International Collaborating Clinics/American College of Rheumatology (SLICC/ACR) Damage Index score	Yes	None
Joint Stiffness Duration	Yes	None
Joint Stiffness Severity	Yes	None
Patient's Global Impression of Severity	Yes	5 categories: no symptoms, very mild, mild, moderate, severe
Number of tender joints (from 28-tender joint count)	Yes	None
Number of swollen joints (from 28-swollen joint count)	Yes	None
CLASI Total Activity Score	Yes	CLASI (<10, ≥10)
CLASI Total Damage Score	Yes	None
Complement C3 level	Yes	Low (<90mg/dL); Normal or higher (≥90mg/dL)

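### The LLDAS model omits baseline PGA and uses baseline SLEDAI-2K and prednisone dose only as single cuts at 10: a modest loss of precision on a major secondary endpoint, not an error

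*SAP*

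**What the plan says.** **Status of the endpoint.** Table JAIA.4.1 lists "Proportion of patients achieving a LLDAS response at Week 52" as a major secondary endpoint for 4 mg and again for 2 mg. Both are in the family with controlled type I error (Section 6.6).

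**Definition.** Table JAIA.6.4: "The LLDAS is a composite measure designed to identify patients achieving a state of low disease activity". It requires, at the visit:
- SLEDAI-2K of 4 or less, "with no activity in SLEDAI-2K major organ systems", and no new SLEDAI-2K feature since the previous visit;
- PGA of 1 or less;
- "Current prednisone or equivalent" of 7.5 mg/day or less.

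None of these criteria is a change from baseline.

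**Model.** In Table JAIA.6.6 the principal analysis of "Proportion of patients who achieve a LLDAS" is logistic regression with NRI + MI on the PPCV set, with no footnote on covariates. Section 6.4 therefore applies: "The model will include the following explanatory variables: treatment, baseline disease activity" (SLEDAI-2K cut at 10), baseline corticosteroid dose (cut at 10 mg/day) and five-level region, with Firth's penalty. Section 6.4.1 gives the reason: these are the stratification factors.

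**Related text.** The MMRM keeps the same strata and adds "baseline value, treatment-by-visit interaction, and baseline value-by-visit interaction". Footnote g of Table JAIA.6.6 changes the logistic covariates for corticosteroid sparing. Appendix 2 summarises "Physician's Global Assessment of Disease Activity score", SLEDAI-2K and prednisone dose at baseline as continuous variables.

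**The concern.** When response means being under fixed limits at Week 52, a patient's starting distance from those limits is a natural predictor. The LLDAS model uses little of that information. PGA is absent. SLEDAI-2K is reduced to one cut, so 10 and 20 count alike. Dose is cut at 10 mg/day while LLDAS uses 7.5, so a patient above 7.5 but below 10, who must reduce to qualify, is grouped with patients who already meet that component.

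At stake is some precision and power for two multiplicity-controlled hypotheses, which could be recovered from data already collected.

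**Working it through.** **1. The plan's own figure.** Section 5.2 claims more than 90% power for SRI-4 with 40% versus 57%, 250 per arm (750/3) and 2-sided alpha 0.05. The pooled rate is (0.40 + 0.57)/2 = 0.485.

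z = [0.17·√250 − 1.96·√(2·0.485·0.515)] / √(0.40·0.60 + 0.57·0.43) = (2.688 − 1.385)/0.696 = 1.87, so power is 96.9%.

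The claim reproduces, but it concerns SRI-4 only. The SAP states no power, response rate or prognostic strength for LLDAS.

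**2. Main simulation for LLDAS (inputs assumed).** 250 versus 250, 1,000 trials per setting, Firth logistic regression, Wald test at 2-sided 0.05. Assumed baselines: SLEDAI-2K mean 10 (SD 3.2), PGA mean 56 mm (SD 15), dose mean 6.5 mg/day with 27% at 10 or more; correlations 0.15 to 0.35.
- Planned model: treatment, SLEDAI-2K cut, dose cut, region.
- Expanded model: the same plus continuous SLEDAI-2K, PGA and dose.

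Assumed odds ratios per SD of SLEDAI-2K and of PGA, then per 7 mg of dose: weak 0.84, 0.80; moderate 0.70, 0.64; strong 0.59, 0.51; very strong 0.50, 0.41. The equivalent gain in patients is (z expanded / z planned)² − 1, with z the ratio of the mean estimate to the mean standard error.

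| LLDAS rates | Strength | Power %, planned → expanded | z, planned → expanded | Equivalent patients |
|---|---|---|---|---|
| 25% vs 37% | nil | 81.0 → 81.2 | 2.84 → 2.82 | −1% |
| | weak | 82.6 → 81.2 | 2.88 → 2.87 | −1% |
| | moderate | 85.3 → 87.0 | 2.96 → 3.02 | +4% |
| | strong | 84.1 → 88.9 | 2.95 → 3.08 | +9% |
| | very strong | 87.5 → 92.3 | 3.05 → 3.25 | +14% |
| 20% vs 30% | nil | 71.2 → 71.3 | 2.54 → 2.53 | −1% |
| | weak | 74.8 → 75.0 | 2.60 → 2.61 | +1% |
| | moderate | 74.3 → 74.8 | 2.58 → 2.61 | +2% |
| | strong | 76.1 → 78.9 | 2.65 → 2.75 | +8% |
| | very strong | 78.1 → 83.5 | 2.68 → 2.87 | +15% |

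The simulation error of one power value is about √(0.82·0.18/1000) = 1.2 points, so the weak-effect dip is not a real loss. With no treatment effect (25% in both arms), rejection was 4.3 to 5.6% for the planned model and 4.1 to 5.3% for the expanded one.

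**3. Other assumptions.**
- 26% vs 36%, log dose, 4,000 trials per setting, weak/moderate/strong slopes: 66.2 → 66.6, 66.1 → 67.4 and 68.7 → 72.3, worth 1%, 4% and 8% more patients. The same change for SRI-4 gained under 1 point.
- No assumed slopes; correlated baseline and Week 52 components put through fixed limits, about 22% vs 31%. At baseline-to-Week-52 correlations of 0.2, 0.35, 0.5 and 0.65, power went 54.9 → 55.7, 55.1 → 56.4, 56.9 → 59.1 and 60.7 → 65.5 (about 1%, 2.5%, 6% and 10% more patients).
- Non-responder imputation in an assumed 30%, unrelated to baseline, at 26% vs 36%: gains of 1%, 4% and 10% without it fall to 1%, 3% and 6% (0.1, 0.8 and 3.3 power points).

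**4. Limits.** The main simulation generates and fits the same linear terms, which favours the expanded model. Its doses move in 2.5 mg steps, so nobody lies strictly between 7.5 and 10 mg/day, and it says nothing about the mismatch between the dose cut and the LLDAS limit.

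**The case against.** The strongest reply is that no error is shown. Adjusting for the stratification factors is a valid choice with a stated reason, and a common model across binary endpoints has value. This stands: the point concerns efficiency only.

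The other objections:
- **Unused baselines.** A reader might infer that all three measures are ignored. They are not: SLEDAI-2K and dose are partly used through the strata, and only PGA is wholly absent.
- **Inconsistency with the MMRM.** A reader might see a contradiction. There is none. The MMRM adds the baseline of its own response, and LLDAS has no such analysed baseline. The Cox model for severe flare and the ANOVA for global impression of change also use only strata and region. The MMRM and footnote g show only that tailoring covariates fits the plan.
- **Lost alpha.** A reader might infer that a weaker LLDAS test starves later hypotheses. The graph in Figure JAIA.6.1 is not reproduced in the text at hand, so the position and alpha of LLDAS cannot be checked.
- **Small gain.** This stands for weak to moderate effects. Encouraged tapering to 7.5 mg/day or less by Week 40 (Section 5.1) may also weaken baseline dose as a predictor.
- **Missing baseline PGA.** This stands. LLDAS needs PGA only at the visit, so a complete-case fit with baseline PGA could drop mITT patients. A handling rule is required.
- **Selectivity.** Corticosteroid sparing also has an absolute dose limit. That endpoint was not simulated and no claim is made about it.

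**Conclusion.** The point holds as a modest, optional improvement in precision. The LLDAS model leaves out baseline PGA and coarsens SLEDAI-2K and dose, although all three define the endpoint.

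Under assumed rates and prognostic strengths, the gain is about 0 to 2 power points (0 to 4% more patients) for weak to moderate effects. In the main simulation it is 2.8 to 5.4 points for strong to very strong effects. Across the settings with stronger effects it is worth about 6 to 15% more patients, the lower end arising with heavy non-responder imputation.

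Two stronger conclusions are not supported. The planned test is not invalid: type I error was close to nominal under both models. Nor can LLDAS be called underpowered, because the SAP gives no LLDAS assumptions against which to judge that.

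**What to change.** Before unblinding, add a Table JAIA.6.6 footnote for LLDAS:
- keep treatment, the two stratification factors and region, with Firth estimation;
- add baseline PGA, baseline SLEDAI-2K and log(prednisone dose + 1) as continuous covariates;
- fill any missing baseline covariate by a simple rule blind to treatment, such as the overall baseline mean, so that no mITT patient is dropped;
- keep the Section 6.4 model as a supplementary analysis.

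Section 6.4.2.4 names only treatment arm and the stratification variables as imputation covariates. The added baselines should be named there too for the LLDAS components, so that imputation and analysis agree.

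Cost: a footnote and a few lines of code, with no new data. The LLDAS odds ratio becomes conditional on more covariates than the SRI-4 one; in the 25% vs 37% simulation it moved from 1.84 to 1.89 at moderate strength and from 1.92 to 2.13 at very strong. If the data are already unblinded, the expanded model belongs only in a labelled supplementary analysis.

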6.3 Definition of Baseline and Postbaseline Periods

For efficacy analyses (excluding daily diaries), baseline is defined as the last non-missing value prior to the first dose of study drug, unless otherwise specified. In most cases, this will be the measurement recorded at Week 0 (Visit 2).

Baseline for the safety analyses is defined as:

- The last non-missing scheduled (planned) measurement prior to the first dose of the study drug for continuous measures by-visit analyses, and
- All non-missing measurements prior to the first dose of the study drug for all other analyses.

In general, for efficacy and safety (except adverse events) analyses, when the baseline measurement is collected on the same day (where time is not collected) as the first dose date, this measurement will be used as the baseline value for data analysis.

Postbaseline measures for the safety analyses are defined as the non-missing scheduled (planned) measurements after the first dose of the study drug for continuous measures by-visit analyses and all non-missing measurements after the first dose of the study drug for all other analyses.

Postbaseline data collection begins after the first dose of study drug administration at Visit 2 (Week 0) and will continue through Visit 16 (Week 52), early study termination visit, or the follow-up visit.

The baseline value for the daily diary assessments (Worst Pain Numeric Rating Scale [NRS], Worst Joint Pain NRS, Worst Fatigue NRS, Joint Stiffness Duration, Joint Stiffness Severity NRS, and Patient Global Impression of Severity [PGI-S]) is defined as the average of the non-missing assessments in the last 7 days prior to the date of first study drug administration (expected at Week 0, Visit 2). There must be at least 4 non-missing daily measurements in the 7 days indicated. If there are less than 4 non-missing daily assessments collected prior to the date of first study drug administration, then the baseline value will be designated as missing. If there are multiple assessments collected on the same day, only the first collected record will be used.

Postbaseline values of daily diary assessments collected after first study drug administration through Visit 16, or early study termination visit, will be defined as the average of the last 7 days prior to the date of the study visit. If less than 4 non-missing daily measurements are present, the visit will be set to missing.

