Worst Fatigue NRS	This Worst Fatigue NRS is a patient-administered 11-point horizontal scale anchored at 0 (no fatigue) and 10 (fatigue as bad as you can imagine)	Worst Fatigue NRS Score	Calculated by averaging data for all available daily diary entries for a 7-day period prior to the visit, not inclusive of the clinic visit day.	Missing if fewer than 4 available daily measurements in the relevant 7 days
Joint Stiffness Duration	This patient-administered scale captures information on the self-reported length of time, in minutes, that a patient's joint stiffness lasted each day.	Joint Stiffness Duration	Calculated by averaging data for all available daily diary entries for a 7-day period prior to the visit, not inclusive of the clinic visit day.	Missing if fewer than 4 available daily measurements in the relevant 7 days
Joint Stiffness Severity NRS	This Joint Stiffness Severity NRS is a single-item patient-administered 11-point horizontal scale anchored at 0 (no joint stiffness) and 10 (joint stiffness as bad as you can imagine)	Joint Stiffness Severity NRS Score	Calculated by averaging data for all available daily diary entries for a 7-day period prior to the visit, not inclusive of the clinic visit day.	Missing if fewer than 4 available daily measurements in the relevant 7 days
Patient Global Impression of Severity	The Patient's Global Impression of Severity is a single-item question asking the patient how they would rate their overall lupus symptoms over the last 24 hours.	Patient Global Impression of Severity Score	Possible values are: (0) No symptoms, (1) Very mild, (2) Mild (3) Moderate (4) Severe	Missing if fewer than 4 available daily measurements in the relevant 7 days
Patient's Global Impression of Change - Lupus	The Patient's Global Impression of Change is a single-item question asking the patient how they would rate their overall lupus symptoms since the start of the study.	Patient's Global Impression of Change Score	Possible values are: (1) Very much better (2) Much better (3) A little better (4) No change (5) A little worse (6) Much worse (7) Very much worse	Single item; missing if missing.

Description and Derivation of Efficacy/Health Outcomes Measures and Endpoints

Measure	Description	Variable	Derivation/Comment	Definition of Missing

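### The ANOVA for Patient Global Impression of Change is valid, but it omits baseline Patient Global Impression of Severity, an already collected covariate that could add a little precision

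*SAP*

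**What the plan says.** SAP Section 6.4 takes three outcomes out of the general MMRM: the SLICC/ACR Damage Index, Patient's Global Impression of Change and Joint Stiffness Duration. For the first, "Treatment comparisons of SLICC/ACR Damage Index will be made using analysis of covariance (ANCOVA) with baseline value as covariate". For the second, "For Patient's Global Impression of Change, the analysis of variance (ANOVA) will be applied". The factors shared by the two models begin: "For both models, treatment, baseline disease activity (total SLEDAI-2K <10; ≥ 10), baseline corticosteroid dose"; region completes the list. The change rating is therefore adjusted for the stratification factors and for nothing the patient reported at baseline.

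Table JAIA.6.4 (Section 6.10.1) describes the two patient global items:

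- **Change:** one question "asking the patient how they would rate their overall lupus symptoms since the start of the study", scored "1) Very much better (2) Much better (3) A little better (4) No change (5) A little worse (6) Much worse (7) Very much worse".
- **Severity:** a "single-item question asking the patient how they would rate their overall lupus symptoms over the last 24 hours", scored "0) No symptoms, (1) Very mild, (2) Mild (3) Moderate (4) Severe".

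The severity item is a daily diary item. Under Section 6.3 its baseline "is defined as the average of the non-missing assessments in the last 7 days prior to the date of first study drug administration", and it is set to missing when fewer than four daily entries exist. Appendix 2 lists it among the baseline summaries, so the variable will be derived in any case.

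Table JAIA.6.6 places the change rating among the secondary endpoints (PP datapoint set, ANOVA with mLOCF, Week 52). Table JAIA.4.1 puts it in the group without multiplicity control. Change in the severity item has its own MMRM.

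**The concern.** The other continuous efficacy outcomes that the SAP analyses with a linear model, whether MMRM or the SLICC/ACR ANCOVA, carry a baseline value. The change rating does not, because a question about change since study start has no baseline of its own. Yet a close relative exists: the same patient rates the same construct on the severity item before the first dose. A patient who starts with very mild symptoms has less room to feel very much better than one who starts severe, so baseline severity plausibly predicts the Week 52 rating. The only disease-activity term in the model is SLEDAI-2K cut at 10, which is a different instrument reduced to two levels.

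What is at stake is precision. Any outcome variation that baseline severity could explain stays in the residual error, and a chance difference between arms in baseline severity is left uncorrected in the estimate.

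**Working it through.** **The plan's own figure.** The SAP gives no power or precision figure for the change rating. Its only power statement (Section 5.2) concerns SRI-4: above 90% for 40% versus 57%, about 750 patients randomized 1:1:1 (250 per arm), two-sided alpha 0.05. With mean proportion 0.485:

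- z = [0.17 × √250 − 1.96 × √(2 × 0.485 × 0.515)] / √(0.40 × 0.60 + 0.57 × 0.43) = (2.688 − 1.385) / 0.696 = 1.87
- Power = 96.9%. The 90% target needs 180 per arm (192 with continuity correction).

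The statement reproduces, and this point does not affect it.

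**Inputs for the change rating.** N = 750, 250 per arm (Section 5.2). The current model has 9 parameters: intercept 1, treatment 2, SLEDAI-2K 1, corticosteroid dose 1, region 4. The correlation r is not in the SAP, so a range is assumed. It must be the partial correlation between baseline severity and the Week 52 rating given the factors already in the model, because only that part is new information.

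**Formulas.**

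- Standard error multiplier = √(1 − r²)
- Equivalent extra patients = 750 × [1/(1 − r²) − 1]
- Power, for an effect that has 80% power without the covariate = Φ[(1.960 + 0.842)/√(1 − r²) − 1.960]

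| Assumed partial r | SE multiplier | SE reduction | Extra patients on 750 | Power (from 80%) |
|---|---|---|---|---|
| 0.1 | 0.995 | 0.5% | 8 | 80.4% |
| 0.2 | 0.980 | 2.0% | 31 | 81.6% |
| 0.3 | 0.954 | 4.6% | 74 | 83.6% |

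**Cost if r is near zero.** Residual degrees of freedom fall from 750 − 9 = 741 to 740. The standard error grows by √(741/740) = 1.0007, or about 0.07%.

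**Is the range reasonable?** An illustrative simulation let baseline severity act only by capping the possible change rating. Under two assumed distributions over severity categories 0 to 4 (2/8/25/45/20% and 5/15/30/35/15%), the correlation was −0.18 and −0.25. That corresponds to about a 2% to 3% smaller standard error, inside the assumed range. Both the distributions and the cap are assumptions, and the simulation did not adjust for the stratification factors.

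**Chance imbalance.** A difference of d standard deviations in baseline severity between two arms moves the unadjusted estimate by about r × d outcome standard deviations. With d = 0.1 and r = 0.2 this is 0.02.

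**The case against.** The case for leaving the plan alone is that nothing in it is wrong. A question about change since study start has no baseline, so ANOVA beside ANCOVA for SLICC/ACR is coherent. The other linear models adjust for their own baseline and none borrows one from another instrument. Randomization makes the unadjusted comparison unbiased. The endpoint is outside the multiplicity control, and the separate MMRM of change in severity already gives a baseline-adjusted analysis of the same concept. All of this stands, and it makes the point an optional gain in efficiency.

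Three stronger readings are tempting, and the SAP does not support them:

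- **That baseline severity fixes what a patient can report.** A reader might infer this from the two scales, but Table JAIA.6.4 sets no such restriction. The change item is a retrospective judgement from study start; the severity item is a 24-hour rating averaged over a week. That a mildly affected patient is less likely to report a large improvement is plausible, and no more than that.
- **That a chance imbalance carries over in full to the treatment difference.** It carries over only in proportion to r. It is not bias, and the confidence interval already allows for such variation.
- **That the simple correlation measures the gain.** The model already contains SLEDAI-2K category, corticosteroid dose and region, so only the partial correlation counts.

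What the objection does not supply is a reason against adding the covariate. It measures the same construct, is taken before treatment, is already derived, and costs almost nothing if it proves uninformative.

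**Conclusion.** The point holds as a small improvement in precision. The ANOVA is valid as written, and no conclusion of the trial depends on changing it. Adding baseline severity would lower the standard error by about 0.5% to 4.6% for a partial correlation of 0.1 to 0.3, with a loss of about 0.07% if the correlation is zero. The size rests on that assumed range, on all 750 patients entering the analysis, and on a roughly linear relation between baseline severity and the change rating. The SAP offers nothing to narrow the range, so the gain is uncertain as well as modest.

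**What to change.** In SAP Section 6.4, and in the matching row of Table JAIA.6.6, replace the ANOVA for Patient's Global Impression of Change with an ANCOVA. Keep treatment and the three stratification factors, and add baseline Patient Global Impression of Severity (the 7-day diary mean of Section 6.3) as a continuous covariate.

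State the rule for missing baselines in the same place: a patient with fewer than four baseline diary entries receives the overall baseline mean, pooled over arms. Without such a rule, a complete-case fit would drop those patients. Because the mean is pooled over arms and uses only pre-treatment data, it does not favour any arm.

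The cost is a line or two of SAP wording and one degree of freedom, with no new data. The change should be written in before unblinding; after that, the adjusted model should appear only as a labelled supplementary analysis. The MMRM for change in the severity item needs no change.
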